4.1 Overall Study Design and Plan

This is a randomized, double-blind, placebo-controlled Phase 3 study consisting of a 6-week DBP to assess the safety, tolerability, PK, and efficacy of cariprazine in subjects from Japan and Taiwan with acute exacerbation of schizophrenia, followed by an 18-week BEP.

This study consists of a screening period, a 6-week DBP, an 18-week BEP, and an 8-week safety follow-up period. The study has a planned enrollment of approximately 250 subjects (125 subjects per arm), randomized on Day 1 (Visit 2) in a 1:1 ratio to placebo or cariprazine 6 mg/day. Subjects who complete the DBP will have the option to enter the 18-week BEP, during which subjects who received placebo during the DBP will be switched to cariprazine 1.5 mg/day and subjects who received cariprazine 6 mg/day during the DBP will receive cariprazine 3 mg/day in a blinded manner in the BEP. Study sites and subjects will remain blinded to treatment assignment for the duration of the study.

The schematic of the study is shown in [Figure 1](#). Further details regarding study procedures are located in the Operations Manual. See Section [5](#) for information regarding eligibility criteria.

Figure 1. Study Schematic

[figure not shown]

Note: The up-titration schedule for the DBP is specified in [Table 1](#).

Screening Period

Subjects who consent to participate in the study will be admitted to the hospital for washout of all prohibited medications (see [Section 5.1](#)) during the screening period and begin screening tests within 7 days after obtaining consent (Visit 1). Ophthalmologic examinations may be started at any time during the screening period but prior to eligibility assessment at baseline (Visit 2).

Figure 2. Study Procedure: Informed Consent, Screening, Day 1 and Week 2

6-Week Double-Blind Period

Subjects will be randomly assigned to receive placebo or cariprazine 6 mg/day for the 6-week DBP. Subjects in the placebo group will receive placebo throughout the 6-week DBP. Subjects in the cariprazine 6 mg/day arm will be dosed based on the dosing schedule in [Table 1](#) in a blinded manner.

Subjects will remain hospitalized at least until Week 2 (Visit 4) to ensure their safety.

Study drug interruption for 1 to 3 days due to study drug tolerability as judged by the investigator (or subinvestigator) is allowed.

Table 1. Dosing Regimen in DBP

	Day 1	Day 2	Day 3	Day 4 – Day 42
Placebo	Placebo	Placebo	Placebo	Placebo

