Cariprazine 6 mg/day	1.5 mg	3 mg	4.5 mg	6 mg

18-Week Blinded Extension Period

Subjects who completed the 6-week DBP are likely to comply with the study protocol and are suitable for participation in BEP as judged by the investigator (or subinvestigator) are eligible to participate in the 18-week BEP of this study.

Subjects in the cariprazine 6 mg/day dosing group in the DBP will receive cariprazine 3 mg/day, and subjects from the placebo group in DBP will receive cariprazine 1.5 mg/day in a blinded manner at Week 6 (Visit 8) after completion of scheduled study activities.

At Weeks 8, 12, 16, and 20, the dose can be increased in 1 step (1.5 mg/day to 3 mg/day or 3 mg/day to 6 mg/day) if the subject meets either of the following dose-escalation criteria after treatment of 2 weeks (Week 8) or at least 4 weeks (Weeks 12, 16, and 20) with stable dose and with no tolerability problem judged by the investigator (or subinvestigator) (optional dose escalation):

- Improvement in SCI-PANSS total score from Day 1 (Visit 2) is < 20% and CGI-S score is ≥ 4
- The investigator's (or subinvestigator's) judgment

The maximum dose of cariprazine is 6 mg/day.

An interruption in dosing of up to 3 days is allowed at any time if the investigator (or subinvestigator) has judged that there is a tolerability problem.

Subjects with a tolerability problem or well-maintained subjects judged by the investigator (or subinvestigator) can reduce the dose by 1 step (6 mg/day to 3 mg/day or 3 mg/day to 1.5 mg/day) in a blinded manner at any visit, including unscheduled visits.

Safety Follow-Up Period

Subjects will enter the 8-week safety follow-up period after the last dose of study drug in the study (either DBP or BEP).

Switching to Another Antipsychotic After Completion of Study Treatment

In switching to another antipsychotic after completion of study treatment, the use of antipsychotics should be limited to only 1 atypical antipsychotic, and the dose should be increased according to

symptoms after at least 1 week of treatment with the antipsychotic agent at the initial dose recommended.

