4.2 Discussion of Study Design

Choice of Control Group

The 6-week DBP utilizes a placebo control group and a cariprazine 6 mg/day group. The use of placebo control is critical to the study design, allowing for further characterization of the safety profile of cariprazine while also ensuring that results assessing efficacy can be interpreted. In this study, a placebo treatment group is included to comply with worldwide regulatory preferences,^{1,2} since placebo-controlled superiority trials have been shown to be conducive to higher quality studies and to provide more reliable outcomes.¹⁻³ Additionally, from a scientific point of view, randomized double-blind comparisons versus placebo are needed to permit adequate evaluations of efficacy. Comparison to a placebo treatment is also of value for distinguishing disease manifestations from adverse reactions of the investigational product.⁴ Participants who are randomized to cariprazine treatment should demonstrate a greater reduction in mean SCI-PANSS total score after 6 weeks compared to those randomized to placebo for the treatment to be considered effective.

The 18-week BEP utilizes 3 dose levels of cariprazine (1.5 mg/day, 3 mg/day, and 6 mg/day) to evaluate the safety, efficacy, PK, and tolerability in subjects from Japan and Taiwan across the dose range approved globally for cariprazine. The investigators and subjects will be blinded throughout the period to keep treatment assignment in DBP blinded.

Appropriateness of Measurements

Standard statistical, clinical, and laboratory procedures will be utilized in this study. All efficacy and safety-related measurements in this study are standard for assessing disease activity in subjects with schizophrenia. All clinical and laboratory procedures in this study are standard, generally accepted, and consistent with prior cariprazine studies.

Suitability of Subject Population

The eligible population for this study in subjects from Japan and Taiwan reflects the approved population for cariprazine use in the US, EU, and other countries and aligns with the key eligibility criteria used in previous cariprazine clinical studies.

Selection of Doses in the Study

The selected cariprazine dosages for this study are 6 mg/day for the DBP and 1.5, 3, and 6 mg/day for the BEP.

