4.0 Analysis Populations

The following population sets will be used for the analyses.

Modified Intent-To-Treat (mITT) Population

The Modified Intent-To-Treat (mITT) population includes all randomized subjects who receive at least 1 dose of study drug and have both baseline and at least 1 postbaseline value of SCI-PANSS total score during the DBP. The mITT population will be used for all efficacy analyses for the DBP. Subjects will be included in the analysis according to the treatment group to which they were randomized (as randomized).

Safety Population

The safety population includes all randomized subjects who receive at least 1 dose of study drug. Subjects will be included in the treatment group corresponding to the double-blind treatment they actually receive in the safety population. The safety population will be used for demographic and safety analyses for the DBP. A subject's actual treatment

group will be determined by the kit type dosed most frequently during the DBP as follows:

- Placebo dose card: Placebo
- 3.0 mg dose card or 3.0 mg titration card: 3.0 mg/day (only for summaries described in Section 2.2)
- 6.0 mg dose card or 6.0 mg titration card: 6.0 mg/day

Kit types in the RN_KIT dataset will be described in the Statistical Programming Plan (SPP).

BEP Population

The BEP population will consist of all subjects who complete the 6-week DBP and take at least 1 dose of study drug during the BEP regardless of which treatment group they were randomized to during the DBP. Subjects will be grouped according to their modal (most frequent) daily dose during the BEP. The BEP population will be used for efficacy and safety analyses for the BEP.

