10.0 Safety Analyses

10.1 General Considerations

Safety data during the DBP and BEP will be summarized for the safety population and BEP population, respectively. Safety summaries during the DBP and BEP will be presented by treatment group (modal daily dose for BEP), including a total group for all subjects on active study treatment, respectively.

Safety data during the Safety Follow-up Period will be summarized for the safety population. The double-blind treatment subjects actually received during the DBP and modal daily dose during the BEP correspond to the treatment groups that will be used for summaries of safety data during the Safety Follow-up Period for subjects who did not enter the BEP and subjects who entered the BEP, respectively. The Safety Follow-up Period starts the day after the last dose of study drug in the study (either during the DBP or BEP).

Unless otherwise specified, safety data will be summarized by period.

For all safety endpoints, the data from subjects who were randomized to cariprazine 3 mg/day prior to removal of this dose arm from the DBP will be included in analyses of the DBP.

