10.2.1 Treatment-Emergent Adverse Events and Newly Emergent Adverse Events

Treatment-emergent AEs (TEAEs) are defined as any AE with an onset date that is on or after the first dose of study treatment and no more than 30 days after the last dose of study drug. TEAEs for the DBP will be defined as any AE with an onset date that is on or after the first dose of DBP study drug and before the first dose of BEP study drug for subjects who participate in the BEP, or on or before the last dose of DBP study drug for subjects who participate in the Safety Follow-up Period (and not in BEP), or within 30 days after the last dose of DBP study drug for subjects who do not participate in either BEP nor Safety Follow-up Period. TEAEs for the BEP will be defined as any AE with an onset date that is on or after the first dose of BEP study drug and on or before the last dose of BEP study drug for subjects who participate in the Safety Follow-up Period, and within 30 days after the last dose of BEP study drug for subjects who do not participate in Safety Follow-up Period. AEs during Safety follow-up are defined as any AE with an onset date during the Safety Follow-up Period after the DBP and BEP. All TEAEs will be summarized overall, as well as by primary MedDRA SOC and PT. The SOCs will be presented in alphabetical order, and the PTs will be presented in alphabetical order within each SOC. All AEs during Safety follow-up will also be summarized in the same manner as TEAEs.

Unless otherwise specified, TEAEs will be summarized during the DBP and BEP, respectively, and AEs during Safety follow-up will be summarized during the Safety Follow-up Period.

The number and percentage of subjects experiencing TEAEs will be summarized. The number and percentage of subjects experiencing AEs during Safety follow-up will be summarized.

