10.2.3 Treatment-Emergent Adverse Events by SOC and/or PT

TEAEs and AEs during Safety follow-up will be summarized by SOC and PT; SOC and PT with a reasonable possibility of being related to study drug as assessed by the investigator; by maximum severity and SOC and PT. Specific AEs will be counted once for each subject for calculating percentages, unless stated otherwise. In addition, if the same AE (SOC or PT) occurs multiple times within a subject, the highest severity and level of relationship to study drug will be reported.

In addition, TEAEs will be summarized by PT and treatment group (modal daily dose for BEP) and sorted by decreasing frequency for the total active group. AEs during Safety follow-up will also be summarized.

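### Extension-period adverse events are tabulated by modal daily dose, so an event that began on 6 mg can be reported in a lower-dose column

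*SAP*

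**What the plan says.** SAP 4.0 defines the BEP groups: "Subjects will be grouped according to their modal (most frequent) daily dose during the BEP". Protocol 7.2 uses the same grouping. SAP 10.1 applies it to all BEP safety summaries: "Safety summaries during the DBP and BEP will be presented by treatment group (modal daily dose for BEP". It adds a total active column and carries the grouping into the safety follow-up for subjects who entered the BEP. SAP 10.2.3 repeats it for the preferred-term tables: "TEAEs will be summarized by PT and treatment group (modal daily dose for BEP) and sorted by decreasing frequency for the total active group".

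SAP 10.2.1 assigns an event to the BEP by its onset date: "any AE with an onset date that is on or after the first dose of BEP study drug". Onset date therefore decides the period, but nothing in the SAP uses it to decide the dose. SAP 6.0 summarizes mean daily dose, final daily dose and patient-years, each by modal dose. SAP 10.2.4 plans listings of serious events, events leading to discontinuation and fatal events, and SAP 10.2.5 plans listings of selected events of special interest. Neither section names dose at onset as a field. No rule is given for ties in the modal dose.

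On dosing, Protocol 4.1 says that "subjects who received placebo during the DBP will be switched to cariprazine 1.5 mg/day", and that the former 6 mg arm starts the BEP on 3 mg. One-step increases are optional at Weeks 8, 12, 16 and 20. Reductions are allowed at any visit, including unscheduled ones: "Subjects with a tolerability problem or well-maintained subjects judged by the investigator (or subinvestigator) can reduce the dose by 1 step". Protocol 4.2 gives the purpose: "The 18-week BEP utilizes 3 dose levels of cariprazine (1.5 mg/day, 3 mg/day, and 6 mg/day) to evaluate the safety, efficacy, PK, and tolerability".

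**The concern.** Modal dose is known only when the subject's BEP exposure has ended. It therefore depends partly on what follows an adverse event. No subject in the current arms starts the BEP on 6 mg, so everyone who reaches it has already built up days on a lower dose. A step down or stop after an event on 6 mg limits the 6 mg days and can leave a lower dose as the mode. The event is then tabulated under a dose that the subject was not taking when it began.

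What is at stake is how the BEP dose columns are read. The protocol says that the three doses are there to evaluate safety and tolerability. Akathisia and extrapyramidal symptoms are events of special interest (Protocol 6.1) and are plausible reasons for stepping down. A reader who takes the three columns as a dose comparison could misjudge tolerability on 6 mg.

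**Working it through.** The documents give no figure on this point, so there is none to reproduce. The check applies the dosing rules to the modal-dose definition.

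**Inputs (Protocol 4.1 and Appendix D).** BEP length is Day 43 to Day 169: 169 − 43 = 126 days. Weeks 8, 12, 16 and 20 fall 14, 42, 70 and 98 days after BEP start. The starting dose is 3 mg (former 6 mg arm) or 1.5 mg (former placebo arm).

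**Assumptions.** Nominal visit days, no interruptions, no re-escalation and no second reduction. The current protocol gives no BEP starting dose for subjects randomized to the withdrawn 3 mg arm, so they are not enumerated.

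**Formulas, former 6 mg arm.** Let *p* be the days on 3 mg before the increase and *d* the days on 6 mg.
- Stops after *d* days: the column is 3 mg if *d* < *p*, tied if *d* = *p*.
- Reduced to 3 mg after *d* days and completes: days on 3 mg = *p* + (126 − *p* − *d*) = 126 − *d*. The column is 3 mg if *d* < 126 − *d*, that is *d* ≤ 62, with a tie at 63.

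The former placebo arm works the same way with days on 1.5 mg added. On its fastest route (14 days on 1.5 mg, 28 on 3 mg), stopping gives a lower column if *d* ≤ 27. Reduction gives 28 + (84 − *d*) = 112 − *d* days on 3 mg, so the column is lower if *d* ≤ 55.

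| Route to 6 mg | Days before 6 mg | Days available on 6 mg | Stops: lower column if *d* ≤ | Reduced to 3 mg: lower column if *d* ≤ |
|---|---|---|---|---|
| Former 6 mg arm, Week 8 | 14 on 3 mg | 112 | 13 (tie 14) | 62 (tie 63) |
| Former 6 mg arm, Week 12 | 42 on 3 mg | 84 | 41 (tie 42) | 62 (tie 63) |
| Former 6 mg arm, Week 16 | 70 on 3 mg | 56 | 56 (all) | 56 (all) |
| Former 6 mg arm, Week 20 | 98 on 3 mg | 28 | 28 (all) | 28 (all) |
| Former placebo, Weeks 8 and 12 | 14 on 1.5, 28 on 3 | 84 | 27 (tie 28) | 55 (tie 56) |
| Former placebo, Weeks 8 and 16 | 14 on 1.5, 56 on 3 | 56 | 55 (tie 56) | 55 (tie 56) |
| Former placebo, Weeks 8 and 20 | 14 on 1.5, 84 on 3 | 28 | 28 (all) | 28 (all) |
| Former placebo, Weeks 12 and 16 | 42 on 1.5, 28 on 3 | 56 | 41 (tie 42) | 41 (tie 42) |
| Former placebo, Weeks 12 and 20 | 42 on 1.5, 56 on 3 | 28 | 28 (all) | 28 (all) |
| Former placebo, Weeks 16 and 20 | 70 on 1.5, 28 on 3 | 28 | 28 (all) | 28 (all) |

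**Totals.** The available days sum to 560 route-by-day combinations. With stopping, 345 fall in a lower column (345/560 = 62%), 5 tie and 210 stay under 6 mg. With reduction, 443 fall lower (443/560 = 79%), 5 tie and 112 stay. These are unweighted counts of possibilities and not probabilities.

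**One subject.** 14 days on 3 mg, raised at Week 8, akathisia after 14 days on 6 mg, then 98 days on 3 mg. Days on 3 mg = 14 + 98 = 112, against 14 on 6 mg. The event that began on 6 mg is reported under 3 mg.

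**The other direction.** A subject with an event in the first 14 days on 3 mg who is raised at Week 8 and stays there has 112 days on 6 mg against 14 on 3 mg. That event is reported under 6 mg.

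**The case against.** The strongest reply has five parts.

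*The shift is conditional.* This stands. A subject raised at Week 8 who stops after 15 or more days on 6 mg stays in the 6 mg column: 98 of the 112 possible stopping days on that route.

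*Part of the misplacement is not caused by the event.* This also stands. A former 6 mg-arm subject raised at Week 16 or 20 is in the 3 mg column even after tolerating 6 mg to the end. The event is still shown under a dose not taken at onset, but the reason is late escalation.

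*The direction is not settled.* A reader might infer that the modal-dose table must flatten or reverse a rising dose relationship. The documents do not support that, because they give no escalation, event or step-down rates. Simulation with assumed inputs shows both outcomes. All runs below take a 20% chance of escalation at each allowed visit. With the 6 mg hazard twice that on 1.5 mg, 50% stepping down and 20% stopping after a first event, the percentages with an event at 1.5/3/6 mg were 26/22/17, a reversal. With 30% stepping down, 10% stopping and later re-escalation allowed, they were 22/22/23. Raising the hazard ratio to 3 in that last case gave 23/27/31, the correct order.

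*The BEP is not the only multi-dose safety source.* Correct. SAP 2.2, 4.0 and 10.1 keep the withdrawn 3 mg arm in the double-blind tables beside 6 mg and placebo, grouped by treatment received and free of this problem. The BEP remains the only period in which 1.5 mg is an assigned maintenance dose and dose changes are allowed.

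*The total active column and the listings are enough.* This does not stand. The total column is unaffected but says nothing about dose, and the listings do not name dose at onset.

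**Conclusion.** The concern holds as a conditional statement: under the SAP's grouping an event that began on 6 mg can be reported in a lower-dose column, and no planned display shows the dose at onset. The day limits rest only on the protocol's nominal schedule and the assumptions listed. A reader might infer that every 6 mg event leading to reduction or stopping is misplaced. The table of routes shows that this goes too far.

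The net size cannot be fixed from the documents. Across assumed inputs (20–40% escalation per allowed visit, 6 mg hazard 2–3 times that on 1.5 mg, 30–70% stepping down and 10–20% stopping), about a third to two thirds of first events on 6 mg appeared in a lower column. With no dose changes the effect is zero. SAP 1.0 reports 34 randomized. If 30 entered the BEP, an upper-end guess, similar inputs give about 2 to 5 first events on 6 mg, of which about 1 to 3 are misplaced. In columns that small, one moved event changes a percentage visibly, but counts this low do not justify making dose-at-onset rates the main safety tables. This is a cheap improvement.

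**What to change.** In SAP 10.2, for the BEP:

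1. Add a supplementary summary of treatment-emergent events, events of special interest and events leading to discontinuation by dose at onset, defined as the last dose taken on or before the onset date. Show patient-years at each dose beside the counts.
2. Add dose at onset as a field in the listings planned in SAP 10.2.4 and 10.2.5.
3. Footnote the modal-dose safety tables: they do not show dose at onset and should not be read as a dose–adverse event relationship.

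Keep the modal-dose tables as planned. The dosing rules are not affected.

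The cost is SAP wording and one small extra table set from dosing and event dates already collected. Rates will be imprecise with so few subjects, and one subject can contribute time to more than one dose. Dose at onset is not causal attribution either: former 6 mg-arm subjects begin the BEP on 3 mg directly after 6 mg, and an event in those first days would be shown under 3 mg.

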5.6 Follow-Up After Subject Discontinuation of Study Drug or from Study

Subjects who discontinue study treatment during the DBP or the BEP of the study will undertake the examinations and observations for the PD visit. Allowable time window for scheduled examination is within 3 days from the last administration of study drug (or within 14 days for the ophthalmologic examination). Subjects who discontinued study treatment during the DBP or the BEP will enter the safety follow-up period. For subjects who prematurely discontinue the safety follow-up period, the visit window for the PD visit is within 7 days after discontinuation.

If a subject prematurely discontinues study participation (withdrawal of informed consent), the procedures outlined for the PD visit should be completed within 3 days of the last administration of study drug. Subjects should be advised on the continued scientific importance of their data even if they discontinue treatment with study drug early. In addition, if a subject is willing, a 30-day follow-up phone call after the last dose of study drug may be completed to ensure all treatment-emergent AEs (TEAEs)/serious adverse events (SAEs) have been resolved.

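### Safety Follow-up percentages keep non-participants in the denominator while SAP 10.2.1 assigns their events up to 30 days after the last dose to the DBP or BEP tables

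*SAP*

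**What the plan says.** SAP 10.1 sets the base for this period: "Safety data during the Safety Follow-up Period will be summarized for the safety population". SAP 4.0 defines that base by dosing alone: "The safety population includes all randomized subjects who receive at least 1 dose of study drug". SAP 10.1 opens the period by date for everyone: "The Safety Follow-up Period starts the day after the last dose of study drug in the study". Its columns are the DBP treatment received for subjects who did not enter the BEP, and the BEP modal daily dose for those who did.

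SAP 10.2.1 gives the statistic, "The number and percentage of subjects experiencing AEs during Safety follow-up will be summarized", and the events that count, "AEs during Safety follow-up are defined as any AE with an onset date during the Safety Follow-up Period after the DBP and BEP". The same section separates subjects by participation. For participants, the DBP or BEP treatment-emergent window closes at the last dose. For non-participants it is extended: after the DBP, "within 30 days after the last dose of DBP study drug for subjects who do not participate in either BEP nor Safety Follow-up Period"; after the BEP, "within 30 days after the last dose of BEP study drug for subjects who do not participate in Safety Follow-up Period".

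No section limits the follow-up tables to subjects who entered follow-up. SAP 5.0 (disposition) does not tabulate entry into follow-up, and neither document defines what participating means.

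**The concern.** SAP 10.1 treats follow-up as a date interval that every dosed subject has. SAP 10.2.1 treats it as a phase that a subject may or may not join. When both are applied to a non-participant, the subject remains in the follow-up denominator while an event in the first 30 days after dosing is assigned to the DBP or BEP table. The follow-up percentage is then diluted by people who were not followed.

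The alternative is to let onset date alone decide. That event then meets the follow-up definition as well as the DBP or BEP definition and appears in two tables.

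For safety data, dilution is the less cautious direction. Its size would vary between columns with the amount of consent withdrawal and loss to follow-up. Because entry into follow-up is not tabulated, a reader of the report could not correct the percentages. The later period that does have its own set, the BEP, is summarized only for subjects who took a BEP dose, so the SAP already uses the approach that is missing here.

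**Working it through.** The documents state no follow-up rate and no follow-up denominator count, so there is no figure of the plan to reproduce.

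**Inputs**
- N, safety population: at most 34, the number randomized (SAP 1.0).
- k, dosed subjects who do not participate in follow-up: not given, so shown as a range that includes zero.
- x, subjects with a follow-up adverse event: not given; x = 5 is assumed for illustration.
- Columns: treatment or modal-dose groups (SAP 10.1). Their sizes are not given; 6 and 11 are assumed.

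**Reading A: events are assigned by participation (SAP 10.2.1)**

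Reported % = x/N. Participant-based % = x/(N − k). Ratio = (N − k)/N. Relative understatement = k/N.

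| k (of N = 34) | x/N | x/(N − k) | ratio | understatement |
|---|---|---|---|---|
| 0 | 5/34 = 14.7% | 5/34 = 14.7% | 1.00 | 0% |
| 1 | 14.7% | 5/33 = 15.2% | 0.97 | 2.9% |
| 3 | 14.7% | 5/31 = 16.1% | 0.91 | 8.8% |
| 5 | 14.7% | 5/29 = 17.2% | 0.85 | 14.7% |
| 10 | 14.7% | 5/24 = 20.8% | 0.71 | 29.4% |

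The ratio does not depend on x.

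Single columns (assumed sizes):
- 6 subjects, 2 with events: 2/6 = 33.3%, against 2/5 = 40.0% (k = 1) or 2/4 = 50.0% (k = 2).
- 11 subjects, 3 with events, k = 2: 3/11 = 27.3%, against 3/9 = 33.3%.

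**Reading B: events are assigned by onset date alone (SAP 10.1)**

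Take a non-participant with an event on day 10 after the last dose. It lies inside the 30-day extension, so it is a DBP or BEP treatment-emergent event. It also lies inside the follow-up interval, so it is a follow-up event. One event is counted in two period tables.

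**Scope**

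Under both readings the rule reaches only 30 days. No rule of SAP 10.2.1 moves a non-participant's later event to another period. SAP 10.1 applies the same population to the follow-up counts for the C-SSRS, potentially clinically significant vital signs and visual acuity, although those sections do not write out a percentage base. Continuous summaries report the number of non-missing observations and are not diluted in this way.

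**The case against.** Four arguments carry weight.

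1. **Few subjects may be affected.** Protocol 4.1, 5.6 and Appendix D send subjects into follow-up after the last dose. For those who stop early, "Subjects who discontinued study treatment during the DBP or the BEP will enter the safety follow-up period". If all do so, k = 0 and nothing changes. This stands, and it is why the size is given as a range. It does not remove the issue: the SAP provides for non-participants, Protocol 5.5 for loss to follow-up, and Protocol 5.6 for consent withdrawal with only an optional 30-day call.

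2. **The numerator is not closed to non-participants.** A reader might infer that they can never contribute a follow-up event, so that the rates are certainly too low. The documents do not support that. The start of the period and the definition of its events are by date, SAP 10.2.1 does not say that reassigned events are excluded from follow-up, and the reassignment ends at 30 days, whereas Protocol 6.1 collects events for 8 weeks. What remains is a choice between dilution and double counting.

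3. **The denominator is inferred.** The SAP names a population and does not write out the percentage base. This stands, but it is the ordinary reading of the sentence, and nothing in the safety sections points to another base. The rule on non-missing observations in SAP 7.0 belongs to subject characteristics.

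4. **An attendance-based set selects on behaviour after treatment.** A subject who dies before the first follow-up visit could drop out of the table meant to count that death; SAP 10.2.2 reports deaths within and beyond 30 days for this period only. This stands and shapes the fix. Using all dosed subjects would be defensible if the SAP said so and also removed the overlap between periods.

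**Conclusion.** SAP 10.1 and 10.2.1 do not fit together for subjects who do not participate in follow-up. Following both gives follow-up percentages multiplied by (N − k)/N; following onset date alone counts events within 30 days twice. With N = 34 the relative understatement runs from 0% (k = 0) to 14.7% (k = 5), and one or two non-participants can move a small column by several percentage points or more. These figures assume that all 34 randomized subjects were dosed, that percentages use the safety population as base, and that non-participants add no follow-up events. The value of k is unknown and may be near zero.

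A reader might also infer that the comparison of cariprazine with placebo is distorted. The documents do not support that. Placebo subjects who enter the BEP move into cariprazine dose columns, so the follow-up columns are not a randomized comparison, and Protocol 7.5 rules out hypothesis testing for safety. SAP 10.2.4 also provides listings of deaths and serious events. The matter is one of accurate descriptive safety reporting and should be corrected, but it does not threaten the trial's conclusions.

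**What to change.** In SAP 10.1, define a Safety Follow-up set: safety-population subjects with at least one follow-up visit or contact after the last dose, or a death recorded after the last dose. The premature-discontinuation visit that closes study treatment should not qualify by itself. State whether the optional 30-day call in Protocol 5.6 counts as a contact.

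Use this set as the denominator for all follow-up count and percentage summaries. Use the same definition wherever SAP 10.2.1 refers to participation, and state there that follow-up events are those of subjects in this set, so that each event falls in one period only. Report the number of non-participants per column.

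Cost: a few sentences in the SAP, one population flag and one extra row in the tables. No new data are needed. Reported follow-up rates rise slightly wherever k is above zero. The drawback is that the set depends on attendance after treatment and that one contact is treated like a full 8 weeks; showing the non-participants per column lets the reader judge how much this matters.
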